## Appendix.

PRAM score (Ducharme, 2008)

Signs	0	1	2	3
Suprasternal	Absent	Absent	Present	Present
retractions				
Scalene	Absent	Absent	Present	Present
contractions				
Air entry	Absent	Decreased at	Widespread	Widespread
		bases	decrease	decrease
Wheezing	Absent	Expiratory only	Inspiratory and	Audible
-			expiratory	
O2 saturation	>95	92-94%	90-92%	<92
in room air				

Severity categories:

Mild: 0-3 Moderate 4-7 Severe:  $\geq 8$

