## **Research Methods:**

## Overview of study design:

The aim of the study is to determine if the use of NIV, for children admitted to hospital with an acute exacerbation of asthma, reduces their work of breathing, need for adjunctive medication, length of hospital stay, and need for intubation and mechanical ventilation. Study design will be prospective, randomized and controlled. The tightly fitting face mask necessary for NIV makes it impossible to make this a blinded study.

The principal enrollment criteria will be children over 2 years of age presenting to the ER with acute asthma. After diagnosis, all children are treated with standard therapy (systemic steroids plus 3 doses of inhaled salbutamol and 1 dose of inhaled ipratropium over a 1 hour period then hourly salbutamol). The principal decision between discharge track and admission track will be made at 2 hours after first steroid dose. Admission criteria are based on sequential PRAM scores.

After initial asthma treatment and observation in the emergency room, to determine which patients can be discharged home, those who need admission will be asked to join the study, then consented and randomized. There will be three treatment groups:

- BiPAP: standard steroid dose, hourly salbutamol and BiPAP at 15/5 cm H2O by face mask with rate 10 to 15/min, oxygen as needed.
- CPAP: standard steroid dose, hourly salbutamol and 8 to 10 cm H2O constant pressure by face mask, oxygen as needed.
- Conventional therapy: standard steroid dose plus hourly nebulized salbutamol, nebulized ipratropium q 6 hrly, magnesium sulphate 50 mg/kg IV (4 doses q 6 hrly), loading dose of aminophylline 6 mg/kg IV if no progress, oxygen as needed.

All children will be admitted to a small 3 bed respiratory unit. They will be closely monitored and objectively scored every 4 hours using the PRAM asthma clinical severity score (Pediatric Respiratory Assessment Measure)[18]. End points will be: time to reach room air, time to reach PRAM score <3, numbers requiring intubation and mechanical ventilation and medication use. Those children older than 5 or 6 yrs, will also perform lung function tests twice daily. Projected patient enrollment will be at least 30 in each arm. Estimated study duration is 6 months.

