#### Study summary:

- Identify patients aged ≥ 2 years attending the Emergency Department with a significant acute asthma exacerbation (using criteria above).
- Begin steroids and initial protocolised standard bronchodilator therapy. Observe in ER and score PRAM hourly.
- Research coordinator is informed and provides parents and child with study information to read during the child's period of observation in the ED.
- A decision about study inclusion should be made 2 hours post-steroid administration in children with PRAM of 8 or more.
- Once admission decision has been made, child is eligible for the study. Obtain consent from the parents and assent from child where possible. If the child is too unstable, assent will be explained and collected when the child is capable.

• After consent, participants will be randomized to one of the three treatment arms in blocks of six, using consecutively numbered opaque envelopes stored in the ED.

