#### General care for all three groups:

All three treatment arms will receive the following standard care:

- Oxygen to keep saturations  $\geq$  92% for all three groups.
- Standard course of oral steroid: dexamethasone 0.3mg/kg/dose once daily for 4 consecutive days,
- On-call research coordinator to assess the patients and record data.
- If a patient in any of the treatment groups deteriorates, they will be managed in the usual way with medical review and admission to ICU as required.

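### The Appendix PRAM table, the plan's only scoring key, contradicts itself, so the same bedside signs can fall on either side of the entry threshold of 8 or the recovery threshold of 3.

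*Combined protocol and SAP*

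**What the plan says.** **The key (protocol, Appendix).** The table scores five signs from 0 to 3 and labels totals of 0-3 mild, 4-7 moderate and 8 or more severe. The rows that matter here, in score order 0, 1, 2, 3, are:

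- Suprasternal retractions: "Suprasternal Absent Absent Present Present"
- Scalene contractions: "Scalene Absent Absent Present Present"
- Air entry: "Air entry Absent Decreased at" for scores 0 and 1 (the cell for score 1 continues on the next line with bases), then a widespread decrease under both 2 and 3
- Saturation in room air: "O2 saturation >95 92-94% 90-92% <92"

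The wheezing row has four distinct entries and no conflict.

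**Where the score is used.**

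- Overview of study design: admission rests on sequential PRAM scores, and admitted children are "objectively scored every 4 hours using the PRAM asthma clinical severity score". The same section says that blinding is impossible.
- Study summary: "A decision about study inclusion should be made 2 hours post-steroid administration in children with PRAM of 8 or more".
- Measured Outcomes: the first listed outcome is time to a PRAM of 3 or less. The Overview and the Statistical analysis section both put the cut-off at below 3.
- Sample size calculation: the trial is sized on a 25% reduction in time to a PRAM of 3.
- Statistical analysis: change in the score over time is also analysed.

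**The concern.** A scoring key should give one score for each finding. This one fails in three ways:

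1. **Saturation.** Neighbouring bands overlap and one value has no band.
2. **Air entry.** The order is reversed at the bottom of the row. Absent air entry gets the best score, and a child with normal air entry cannot be scored from the table at all.
3. **Repeated cells, as extracted.** Absent retractions or scalene contractions can score 0 or 1, present ones 2 or 3, and a widespread decrease in air entry 2 or 3.

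A child can therefore be counted as eligible or not, or as recovered or not, with no difference in the signs. Raters know the treatment arm, so any discretion in the score could run differently by arm. Assessments are 4 hours apart, so one borderline reading that defers recovery to the next assessment moves that child's time by 4 hours. The design effect is 12 hours (25% of the 48-hour control mean), so the move is 4/12, or one third of it, for that child. It is not an estimate of bias in the arm mean.

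**Working it through.** **The plan's own figure.** The sample size section gives 26 per arm from a 12-hour difference (48 - 36), SD 16, 80% power and 5% type 1 error. The two-sided normal formula gives n = 2 × (1.96 + 0.84)² × 16² / 12² = 27.9, so 28 per arm, within two of the stated figure (sidedness is not stated). The present point does not depend on this number; it shows only that the PRAM endpoint carries the sizing.

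**Inputs for the check.** All come from the Appendix:

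- retractions: absent or present (2)
- scalene contractions: absent or present (2)
- air entry: the three distinct printed entries (3), the first scored 0
- wheeze: 0, 1, 2 or 3 (4)
- saturation in whole per cent: above 95, 93-94, 92, 90-91, below 90 (5); 95% is left out because it has no score

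Combinations: 2 × 2 × 3 × 4 × 5 = 240. For each, take the lowest and highest total that the table permits and compare them with the cut-offs.

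**Step 1: saturation overlap alone.** Assume that the repeated cells are an artefact and take the lower score for each.

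- Two of the five saturation groups have two scores, so 240 × 2/5 = 96 combinations have two totals, one point apart.
- Let R be the sum of the two retraction rows: 0 in one way, 2 in two ways, 4 in one way. Let S be air entry plus wheeze: the values 0, 1, 2, 3, 4, 5 arise in 1, 2, 3, 3, 2, 1 ways.
- Straddling 3 or less means 3 on the low reading and 4 on the high. At 92% (1 or 2), R + S must be 2: 3 + 2×1 = 5 ways. At 90-91% (2 or 3), R + S must be 1: 2 ways. Total **7**.
- Straddling 8 or more means 7 or 8. At 92%, R + S = 6: 2×2 + 3 = 7 ways. At 90-91%, R + S = 5: 1 + 2×3 + 2 = 9 ways. Total **16**.
- With the recovery cut-off at below 3 (2 or 3), R + S is 1 at 92% (2 ways) or 0 at 90-91% (1 way). Total 3.

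Examples: no retractions or scalene contraction, air entry decreased at the bases, expiratory wheeze and 92% give 0+0+1+1+(1 or 2) = 3 or 4. With both retraction signs present and the rest unchanged, 2+2+1+1+(1 or 2) = 7 or 8.

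**Step 2: the table as extracted, repeats taken as real.**

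- Every combination has at least a 2-point spread, one point from each retraction row. Widespread decrease adds one and an overlapping saturation adds one. The spread is 2 points in 96 combinations, 3 in 112 and 4 in 32.
- 3 or less: 35 qualify on the lowest reading and 4 on the highest, so 35 - 4 = **31** are undecided. At below 3, 15 - 1 = 14.
- 8 or more: 161 qualify on the highest reading and 58 on the lowest, so 161 - 58 = **103** are undecided.

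**Step 3: air-entry order, read literally.** Both retraction signs present, absent air entry, no wheeze and saturation below 90% give 2+2+0+0+3 = 7 with the lower retraction scores and 3+3+0+0+3 = 9 with the higher. At 7 the child is labelled moderate and is below the gate. The counts in steps 1 and 2 use only the fact that the first air-entry cell scores 0, so they do not depend on what that cell was meant to say.

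**The case against.** **The repeated cells may not be on the page.** The repeats are adjacent pairs, the pattern expected if software copied merged cells. This objection stands, and most of the larger figures rest on those cells: without them, 103 falls to 16, 31 to 7 and the 4-point spread to 1. It does not clear the table. Merging cannot produce overlapping saturation limits or put absent air entry under 0, and a cell truly merged across two score columns would still leave its score unclear.

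**Raters may use the published score.** The Overview cites it, the Appendix is labelled as that instrument, and paediatricians staff the unit. This also has force. A reader might infer that PRAM cannot be measured reproducibly in this trial at all. The documents do not show that; they give no rater-agreement figure. Equally, nothing tells raters to prefer the publication to the Appendix.

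**Harm to a child with absent air entry.** A reader might infer a serious safety failure. The documents limit this: impending respiratory failure that needs direct PICU admission is an exclusion, and escalation under General care and Criteria for study termination follows deterioration or signs of impending failure, not a PRAM value. What remains is a mis-ordered score affecting enrolment, the PRAM-based admission decision and the recorded course.

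**Low saturation within the mild band.** A child whose only abnormal item is saturation can total 3. That is a property of any summed score, and time to room air is a separate outcome. It is not an error in the table.

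**Conclusion.** The concern holds as a defect in the scoring key. On the printed saturation and air-entry rows alone, the Appendix gives some findings two scores, leaves 95% saturation and normal air entry without a score, and ranks absent air entry as the best state. The saturation overlap by itself gives 96 of 240 combinations two totals and lets 7 cross the cut-off of 3 or less and 16 the gate of 8. If the page image confirms the repeated cells, the figures are 31 and 103, with spreads of up to 4 points.

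The counts rest on whole-number saturations, on leaving out 95%, and, for the smaller figures, on taking the lower score for each repeat. They weight every combination equally. A reader might take 103 of 240 as the share of children whose eligibility is undecided; the documents give no frequencies of signs, so no such share can be stated.

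The recovery cut-off itself also differs between sections (3 or less against below 3), which changes the recovery counts and needs settling in the same edit. The sample size figure is not altered by this point.

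**What to change.** 1. Check the page image for the repeated cells.
2. Reconcile the Appendix with the published instrument the plan already cites (reference 18), so that each finding has one score, the saturation bands are mutually exclusive and cover every value, and the air-entry 0 cell is corrected against that source.
3. State that the thresholds of 8 and 3 refer to that version, and give one recovery cut-off throughout Measured Outcomes, the Overview, the sample size section and the Statistical analysis section.
4. Brief everyone who scores on that version before further children are scored.
5. If children were already scored on the present table and the individual signs were recorded, re-derive their scores from those signs.

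The cost is a one-page replacement, matching wording in a few sections and a short briefing. No patients, visits or procedures are added. Step 5 costs more only if scoring has begun, and it is possible only if item-level signs were kept, which the documents do not say.
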